**Hypothesis 3:** Pharmacologic  $\alpha 4\beta 2^*$  nAChR activation in PD subjects with cholinergic deficits will improve attentional performance on the SAT. The improvement in SAT performance will correlate with improvement in laboratory measures of gait function and postural control assessed in Specific Aim 2.

Our group possesses unique expertise in preclinical models, nAChR pharmacology, cholinergic imaging, and physiological measures of gait function, postural control, and attention. This project interacts directly with **Project II**, depends on the **Clinical Resource Core**, and is strongly connected to **Project I** preclinical experiments. The potential impact of the proposed experiments is considerable. This work would provide strong support for our *central hypothesis*, establish therapeutic validity of the novel animal model employed in **Project I**, and implement new methodologies for the evaluation of treatments to improve gait and balance deficits in PD. These experiments would identify  $\alpha 4\beta 2^*$  nAChRs as a therapeutic target in a clinically definable PD subgroup, setting the stage for trials of  $\alpha 4\beta 2^*$  nAChR agonists as adjunctive treatments to mitigate balance and gait abnormalities in these patients.

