indicates that  $\alpha 4\beta 2^*$  nAChRs are crucial actors in cholinergic modulation of attention (**Project 1**) (42-46). Consistent with this work, our preliminary preclinical data suggests that stimulation of  $\alpha 4\beta 2^*$  nAChRs improves gait and balance in the novel dual lesion model (**Project 1**). These combined results lead to an important prediction: subacute  $\alpha 4\beta 2^*$  nAChR administration to hypocholinergic PD subjects will improve attentional performance and improved attentional performance will correlate with improved gait and postural control induced by  $\alpha 4\beta 2^*$  nAChR stimulation. Evaluating this prediction is important for assessing the mechanisms by which cholinergic projection system degeneration impairs gait and balance and is important also for assessing the validity of the novel rodent model presented in **Project 1**.

*Preliminary Data:* [name] group developed a robust test of attentional function, the Sustained Attention Test (SAT), for use in rodent experiments, and subsequently adapted and validated the SAT for use in humans (**Project 1**) (111-113). Briefly the SAT consists of a randomized sequence of cued and non-cued (or signal and nonsignal) trials. Responses are hits and misses, and correct rejections and false alarms, respectively. Hits and correct rejections are rewarded. SAT performance reflects frontal cortical cholinergic signaling through  $\alpha 4\beta 2^*$  nAChRs. We evaluated a particularly

relevant version of the SAT including a distractor component (dSAT), in PD subjects who had previously undergone [C]PMP imaging to assess cholinergic projection systems integrity. There was considerable variation in dSAT performance, which was a linear function of cortical cholinergic terminal integrity

(**Figure 6**). These results indicate that dSAT performance in PD directly reflects cortical cholinergic signaling, likely mediated by  $\alpha 4\beta 2^{\circ}$  nAChRs.

*Procedures:* This experiment will be conducted in parallel with those for SA2. Attention will be evaluated with the dSAT at all evaluation points in the double-blind crossover design VCN intervention study described above. We will correlate dSAT changes in response to VCN with gait speed and postural control changes in response to VCN. The sample size is determined from the goals of **SA2**. With this sample size, an effect size of 0.4 can be detected with at least

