80% power and a two-sided Type I error of 0.05 assuming a within-subject correlation of 0.69. Similar statistical methods as those used for SA2 will be employed to test the impact of VCN on dSAT. An exploratory analysis will be conducted to examine medication of treatment effects on gait and other postural outcomes by dSAT. In the presence of a treatment effect, a variable is declared a mediator if it complies with three things: it is affected by the treatment, it predicts the endpoint of interest, and the treatment effect is attenuated when the potential mediating factor is adjusted for. Mediation analysis will be conducted by including mediating factors in the mixed model regression analysis outlined above. Structural equation models will be used to estimate the direct effect of VCN and the indirect effects of the VCN due to mediators, as has been recommended for intervention studies of disease prevention (114,115).

Potential Problems and Alternatives: All procedures, including the dSAT, are well established in our center. Most of the potential problems are discussed above (**SA2** Potential Problems and Alternatives). Our prediction is that improved dSAT performance will correlate with improved gait speed and postural control measures. There may be dissociations between results of dSAT testing and gait speed-postural control outcome measures. Attentional performance may improve but not gait speed and postural control. Gait speed and postural control may improve without commensurate improvements in dSAT performance. These outcomes would be important for evaluating our understanding of how cholinergic deficits degrade gait and postural control. Lack of correlation would direct future research away from attentional mechanisms and towards alternative mechanisms, such as PPN projection roles in sensorimotor integration. We will have

[F]FEOBV data on cholinergic projection systems integrity for all these subjects and secondary analyses looking at specific functional deficits and specific pathway changes may be revealing. Whether or not dSAT

performance response correlates with improvements in gait speed and postural control measures is also important for evaluating the validity of the dual lesion model. It is crucial to know the limitations of this interesting model prior to using it extensively for preclinical evaluations of potential therapies.

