2.2 Scope of the analyses

These analyses will assess the efficacy and safety of varenicline in comparison with placebo, addressing the primary and secondary objectives of the study.

3 Study Objectives and End points

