6.6 Multiple Testing

Two-sided p-values will be reported. For the co-primary endpoints, a Bonferonni adjustment for multiplicity will be applied. For all other endpoints, no adjustments for multiplicity will be made. Thus, p-values for secondary and exploratory outcomes will be interpreted with caution (note that this is a departure from the protocol). Means and standard errors will be provided to summarize treatment differences for efficacy end points.

7 Summary of Study Data

Descriptive summary statistics will be derived for all data at baseline, separately by treatment sequence and overall. For efficacy, exploratory and safety data, data will be presented by treatment group. Treatment group will be characterized as "Varenicline" and "Placebo"; for pooled summaries, "Overall" will be used as the column heading. All tables will be annotated with the total population size relevant to that table/treatment, including any missing observations.

For continuous variables, mean, standard deviation, median, interquartile range, minimum and maximum will be reported. For categorical variables, number and percentages will be reported (excluding missing values). Graphical methods will be heavily used in this pilot study to assess the pattern of response over time for key variables and to assess the relationships among variables.

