8.1 Primary, Secondary and Exploratory Efficacy Analyses

For the Crossover study, linear mixed models containing treatment sequence, treatment period, treatment group, and dependent-variable baseline value, with participant within treatment sequence as a random effect, will be used for analysis of continuous outcomes. To compare differences between VCN and placebo, a test for carryover based on the sequence effect will be conducted using patient with sequence as the error term. Results will be presented as least squares (LS) mean and standard error (SE). The co-primary endpoints will be tested at the 2-sided, 0.025, significance level. All other tests will be based on a 2-sided significance level of 0.05; no adjustments will be made for additional multiple comparisons. Primary, secondary and key efficacy endpoints will be analyzed in all randomized participants (intention-to-treat [ITT] population) and in the Compliant Population.

Additional sensitivity analyses will be performed for UPDSR-III total and PIG subscale scores, where baseline degree of total cortical cholinergic denervation (from PET scans) and baseline degree of striatal dopamine denervation (from PET scans) were incorporated as covariates in separate models. These models will also be run for gait speed end points.

9 Safety Analyses

Safety endpoints will be analyzed in all randomized participants who received at least one dose of study medication (Safety Population). We will include adverse events that occurred in the washout period with the treatment given in period one.

Safety data, including adverse events (AEs) and the Columbia-Suicide Severity Rating Scale (C-SSRS), will be summarized descriptively by treatment group for the Safety Population.

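### The SAP carries forward neither the attention–gait correlation of Hypothesis 3 nor the exploratory mediation analysis, and the protocol's mediation model states no within-person/between-person split

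*Protocol*

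**What the plan says.** Protocol, Specific Aims, Hypothesis 3 has two parts: VCN improves attention, and "The improvement in SAT performance will correlate with improvement in laboratory measures of gait function and postural control assessed in Specific Aim 2". The Procedures of Specific Aim 3 plan the second part directly: "We will correlate dSAT changes in response to VCN with gait speed and postural control changes in response to VCN". They then add: "An exploratory analysis will be conducted to examine medication of treatment effects on gait and other postural outcomes by dSAT" (from context, mediation is meant). That rule applies only once there is a treatment effect. It then asks that VCN changes the mediator, that the mediator is associated with the outcome, and that adjusting for it shrinks the treatment effect. The mediator is added to the mixed model, and structural equation models are to estimate direct and indirect effects.

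The protocol attaches consequences to the correlation. Under Potential Problems and Alternatives for Specific Aim 3: "Lack of correlation would direct future research away from attentional mechanisms and towards alternative mechanisms". Whether dSAT "performance response correlates with improvements in gait speed and postural control measures is also important for evaluating the validity of the dual lesion model".

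SAP 2.2 sets a narrower scope: "These analyses will assess the efficacy and safety of varenicline in comparison with placebo, addressing the primary and secondary objectives of the study". The objectives in 3.1 contain no attention–gait link. The efficacy analysis in 8.1 uses "linear mixed models containing treatment sequence, treatment period, treatment group, and dependent-variable baseline value, with participant within treatment sequence as a random effect", with no attention term. The nearest text, in section 7, offers graphs "to assess the pattern of response over time for key variables and to assess the relationships among variables". Section 6.6 flags one departure from the protocol, on multiplicity.

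**The concern.** There are two problems, and the first carries more weight.

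1. A pre-specified analysis of a stated hypothesis has no definition in the SAP. The attention score is open: Hypothesis 3 names SAT and the Procedures name dSAT, while the SAP makes SAT secondary (4.4.2) and dSAT exploratory (3.2.3). So is the meaning of change in response to VCN. It could be VCN minus placebo, or pre- to post-VCN, which also contains practice and placebo response. These choices could be made after unblinding, on a result that the protocol says would steer research and help to judge the animal model.

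2. In a crossover, a covariate measured in each period varies both between people and within a person. Entered as one term in a random-intercept model, its coefficient is a weighted average of the two associations. Only the within-person part bears on whether a change in attention goes with a change in gait. Patients who attend better may simply walk better in general, and the model could then credit attention with part of a gait gain that it did not carry.

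**Working it through.** **Is either analysis in the SAP?** Objectives (3.1), endpoints (3.2), covariates (6.3) and models (8.1) contain treatment comparisons only. There is no correlation of changes, no mediation model and no statement that either was dropped.

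**The protocol's own power figure.** Inputs (Specific Aim 3, Procedures): effect 0.4, within-subject correlation 0.69, N=33, two-sided 0.05. Paired effect = 0.4/√(2(1−0.69)) = 0.508. Noncentral-t power is 80.8%, so the stated figure of at least 80% reproduces. It covers the VCN effect on dSAT, not the correlation.

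**Precision of the correlation.** Fisher z, with one degree of freedom used for period:
- 95% limits around r=0 are ±tanh(1.96/√(N−4)): ±0.35 at N=33, and ±0.32 at N=38 (42 × 0.9 = 37.8 completers).
- 80% power needs r = tanh(2.80/√(N−4)): 0.48 at N=33, 0.45 at N=38.

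**Effects used for the mediation check.** For gait and JERK the protocol gives N=33, 80% power, alpha 0.025 and correlations of 0.64 and 0.72. The paired effect needed is 0.559.
- Gait: 0.559 × √(2(1−0.64)) = 0.474 SD.
- JERK: 0.559 × √(2(1−0.72)) = 0.418 SD.
- dSAT, solved in the same way at alpha 0.05: 0.396 SD.

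**Why the coefficient is mixed (two visits, no within-person link).** Let c be the assumed correlation between the person-level components of dSAT and gait. In SD units:
- dSAT variance of the within-person difference = 2(1−0.69) = 0.62; of the sum = 2(1+0.69) = 3.38.
- Gait: 2(1−0.64) = 0.72 and 2(1+0.64) = 3.28.
- At c=0.5, covariance of the sums = 4 × 0.5 × √(0.69×0.64) = 1.329, so the between-person slope is 1.329/3.38 = 0.393. The within-person slope is 0.
- Weights: within 0.62/0.72 = 0.861; between 3.38/(3.28 − 0.393×1.329) = 1.226. Between-person share = 1.226/(0.861+1.226) = 0.587.
- Mixed coefficient = 0.587 × 0.393 = 0.231. Gait effect moved to dSAT = 0.396 × 0.231 = 0.091, or 19% of 0.474, although the true share is zero.

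Simulation agrees: the mean adjusted gait effect at c=0.5 is 0.381, against 0.474 − 0.091 = 0.383 here. The misattributed share is still about 20% at N=400, so this is bias and not noise.

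**How often the rule is falsely met.** Simulated crossover at N=33, random-intercept REML with treatment, period and sequence, no within-person link. The rule is total effect p<0.025, VCN effect on dSAT p<0.05, dSAT coefficient p<0.05, and an attenuated treatment effect.

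| Setting | c=0.3 | c=0.5 |
|---|---|---|
| Gait, two visits | 12–13% | 31% |
| Gait, four visits | 10–11% | 21–23% |
| Gait, two visits, outcome baseline added | 7% | 13% |
| JERK, two visits | 12% | 30% |
| JERK, two visits, outcome baseline added | 6% | 11% |
| Gait, two visits, half the effects | 1.5% | 3.3% |
| VCN moves gait but not dSAT | 0.5% | 1.2% |
| VCN moves dSAT but not gait | 0.3% | 0.6% |
| Gait, two visits, person-mean centred | about 2% | about 2% |

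For gait with two visits, the rate is 2% at c=0 and 4% at c=0.1.

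**The case against.** The SAP limits itself to varenicline versus placebo for its primary and secondary objectives. A plan of limited scope does not cancel the protocol, whose commitment to the correlation stands. A reader might infer that Hypothesis 3 was abandoned, and the documents do not say so. This narrows the point to a missing specification, but it does not answer it, because neither document defines the analysis.

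A reader might also infer that the protocol prescribes an uncentred model. It does not: it is silent on centring. It also plans structural equation models, which were not simulated here, so the rates above apply only to the mixed-model rule. The analysis is labelled exploratory, and the SAP leaves it out as well, so the modelling problem arises only if someone runs it.

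The highest rates need the full powered effects, an assumed correlation and two visits. The protocol measures gait and dSAT at four points, and the baseline-adjusted figures combine the protocol's mediator with the SAP's covariate, a model that neither document specifies. Neither document gives the between-person correlation, and selecting hypocholinergic patients may lower it. All of this stands, and the rates are illustrations.

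Finally, the remedies do not remove confounding within a period. If dSAT and gait share a non-causal within-period correlation of 0.3, the centred rule is still met in about 29% of trials and the change correlation is significant in 39%. That also stands.

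**Conclusion.** The omission is established from the text. Followed alone, the SAP cannot answer the second half of Hypothesis 3, and it does not say that this is a departure. Even when the analysis is done, an interval of about ±0.35 around zero at N=33 means that a null result alone cannot rule out a moderate link. It would be weak ground for the redirection of research that the protocol describes.

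The modelling point is conditional. If dSAT is entered as a single covariate and VCN has moved both outcomes, false declarations run at about 12–31% (two visits), 10–23% (four visits) or 7–13% (two visits, outcome baseline added) at assumed between-person correlations of 0.3 to 0.5. They are near 2% or below if the correlation is near zero, if VCN moves only one outcome, or with person-mean centring. These are not forecasts for this trial. The treatment comparisons of the primary and secondary endpoints are unaffected. The change is worth making, but it concerns a mechanistic question and not the main result.

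**What to change.** 1. In the SAP, analyse Hypothesis 3 as the correlation of period-adjusted VCN-minus-placebo differences in one named attention score (SAT or dSAT) with those in gait speed and in JERK. Report r with its 95% interval. Otherwise, state that the analysis was dropped and why.
2. If mediation is run, by mixed model or structural equation model, enter attention as person mean plus within-person deviation, or work with within-person differences. Take the mediator effect from the within-person part only, and keep the analysis exploratory.

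The cost is a short SAP paragraph and one recoded covariate, with no new data. The price is precision: centring raises the standard error of the mediator effect about 1.4- to 1.9-fold. The report should say that neither analysis removes within-period confounding or proves mediation.

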#### Approach

#### Background & Preliminary Data

Cholinergic Neurotransmission & PD Gait Dysfunction: Numerous studies indicate that cognitive dysfunction affects gait and balance functions (reviewed by 33, 34, and in Overview), implicating BF cholinergic degeneration in gait dysfunction in PD. Impaired attention and executive control are risk factors for falling and simultaneous cognitive task (dual-task) demands affect biomechanical parameters of balance and gait in PD patients (35-38). In controls and PD subjects, individuals with attentional/executive deficits are more prone to falls and gait abnormalities (see Project II) (35-39). Degeneration of BF corticopetal projections is well established in PD and the magnitude of BF terminal loss is greater in PD than in AD (15,16,40,41). BF cholinergic projections are crucial for

[figure not shown]

Figure 1: [C]PMP-PET and heterogeneity of cholinergic deficits in PD. [C]PMP-PET imaging of cortical cholinergic terminals in PD. Left image; PD subject with normal cortical cholinergic innervation. Right image; PD subject with diminished cortical cholinergic innervation. neocortical modulation of attention by enhancing detection of relevant cues and filtering distractors (28). As described in considerable work by one participant in this Udall Center application, [name], BF mediated cholinergic neurotransmission regulates attention via modulation of thalamocortical afferent effects on cholinergic presynaptic heteroreceptors (see Project I) (28,42-45). [name] and [name] recent studies in a novel rodent model of combined dopaminergic and cholinergic pathway lesions indicate that this dual lesion paradigm, mimicking the pathology of many PD patients, produces gait and balance abnormalities analogous to those found in PD (Project I Preliminary Data and below) (32, 46).

The mesopontine PPN complex has wide projections to many regions, including other brainstem structures, the cerebellum, and dense connections with the basal ganglia and thalamus (47-50). The PPN

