*Procedures*: The **SA1** experiment will select the VCN dose. Based on discussions with the proposed **Biostatistical and Data Management** co-Core leaders, we will employ a randomized double- blind, placebocontrolled, 2-period, 2-sequence crossover design to assess the effects of subacute VCN administration on gait function, postural control, and attention in PD subjects with cholinergic deficits (**Figure 5**). PD participants will be on stable doses of dopaminergic therapy for 3 months prior to enrollment and continue on their usual Table 3: ISway: data in non-fallers (n=5) and falling PD (n=6). Means +SD.

	Non- Faller	Faller	t-test (p- value)
Jerk	0.082 ±	0.213±	t = -2.0
	0.080	0.125	(0.072)
RMS	0.058±	0.109±	t = -2.3
	0.021	0.045	(0.045)
Velocity	0.114±	0.200±	t =-2.3
	0.050	0.067	(0.049)
Centroid Freq (AP)	0.734±	0.617±	t=2.7,
(AP)	0.160	0.140	(0.026)

schedule of dopaminergic medications for the duration of this study. Individuals with depression and unstable cardiac disease will be excluded. Within-subjects crossover designs were employed successfully in recent VCN trials for AD and mood disorders during smoking cessation (89,90).

We will administer VCN or placebo for 3 weeks, followed by a 3 week washout period, and crossover to placebo or VCN for the 3 week second treatment period. Study visits will be completed within a five business day window before or after the target date. The duration of the treatment and washout periods is based partly on prior human experimental and trial experience (89-95). Mocking et al. detected improved cognitive effects of VCN with a week of treatment (79). We chose a longer period to ensure stable receptor upregulation and because initiation of treatment may require gradual dose incrementing. The washout period is based partly on work by Zhang et al. with another  $\alpha 4\beta 2^*$  nAChR partial agonist in MPTP lesioned non-human primates (71). This group reported an effect of

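### The planned correlation of dSAT change with gait and postural change has no sequence adjustment and no off-drug reference, so a non-zero value need not mean that individual varenicline responses are linked

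*Protocol*

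**What the plan says.** Hypothesis 3 (protocol, Specific Aims) has two clauses. The first is that varenicline (VCN) "will improve attentional performance on the SAT". The second is: "The improvement in SAT performance will correlate with improvement in laboratory measures of gait function and postural control assessed in Specific Aim 2".

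The Specific Aim 3 Procedures give the second clause one sentence of method: "We will correlate dSAT changes in response to VCN with gait speed and postural control changes in response to VCN". The coefficient, the null value, the definition of change, any period or sequence adjustment and any reference correlation are not stated. The same section says "Attention will be evaluated with the dSAT at all evaluation points", so dSAT is taken at the same four evaluations as gait and posture (baseline, end of period 1, end of washout, end of period 2).

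Under Potential Problems and Alternatives for that aim, the protocol writes "Our prediction is that improved dSAT performance will correlate with improved gait speed and postural control measures". It adds that a lack of correlation would turn research away from attentional mechanisms, and that the result bears on the validity of the dual-lesion rodent model. The mediation analysis is exploratory and conditional on a treatment effect; the correlation carries no such condition.

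SAP section 8.1 analyses outcomes with "linear mixed models containing treatment sequence, treatment period, treatment group" and baseline value. The SAP contains no correlation or mediation analysis. It makes SAT without distractor the secondary end point and lists dSAT among the exploratory ones (sections 3.2.2 and 3.2.3).

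**The concern.** The scientific question is whether patients whose attention responds more to the drug also respond more in gait or posture. The observable is the correlation of two paired differences, each the sum of an individual drug response and the noise of two visits. Differencing removes stable differences between patients. It leaves two things.

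- **Shared visit noise.** Alertness, fatigue or medication state on the day can move both measures. The protocol's Background makes this plausible off drug: "simultaneous cognitive task (dual-task) demands affect biomechanical parameters of balance and gait in PD patients".
- **Period shifts.** The study is a "2-period, 2-sequence crossover design to assess the effects of subacute VCN administration on gait function, postural control, and attention". A shift from period 1 to period 2 enters the VCN-minus-placebo difference with opposite signs in the two sequences. If both outcomes shift, this creates a correlation across patients.

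At stake is a mechanistic conclusion. A significant correlation would be read as support for the attentional route and for the animal model, although it could reflect co-movement that occurs without the drug.

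**Working it through.** **Inputs from the documents.** N=33 evaluable (SA2 Sample Size). About 38 remain if 10% of the 42 enrolled drop out (42 × 0.9 = 37.8). Within-subject correlations are 0.69 for dSAT, 0.64 for gait speed and 0.72 for JERK; the dSAT effect size is 0.4.

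**Assumed, because the documents do not give them.** The same-visit residual correlation r_w between dSAT and gait, and the period shift.

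**Plan's own figure.** The documents state no figure for the correlation. The dSAT power statement reproduces: SD of the difference = √(2 × (1 − 0.69)) = √0.62 = 0.787; 0.4/0.787 = 0.508; a paired t-test at N=33, two-sided 0.05, has 80.8% power, against the stated 80% or more.

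**Expected correlation with an inert drug, no period shift.** Write each difference as D_k = e_k(VCN visit) − e_k(placebo visit). Then Cov(D_1, D_2) = 2·r_w·σ_1·σ_2 and Var(D_k) = 2σ_k², so corr(D_1, D_2) = r_w. The residual variances cancel, so the result is the same for gait (1 − 0.64 = 0.36) and JERK (1 − 0.72 = 0.28). For JERK lower is better, so the sign reverses and the two-sided rate does not change.

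**Expected correlation from a period shift alone.** With a shift of δ SDs of the paired difference on both outcomes, the differences carry +δ in one sequence and −δ in the other. At 1:1 allocation the correlation is δ²/(1 + δ²). For δ = 0.5 this is 0.25/1.25 = 0.20.

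**Rejection rates.** The critical |r| at N=33 is 0.344 (two-sided 0.05). Simulations of 20,000 trials per setting, drug inert, residual variances 0.31 and 0.36, gave, to within about one percentage point:

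| Setting | Unadjusted, N=33 | Unadjusted, N=38 | Sequence-adjusted, N=33 |
|---|---|---|---|
| r_w = 0 | 5% | 5% | 5% |
| r_w = 0.1 | 9% | 9% | 8–9% |
| r_w = 0.2 | 20–21% | 22–23% | 20% |
| r_w = 0.3 | 41% | 46% | 39–40% |
| δ = 0.3 only | 7% | 8% | 5% |
| δ = 0.5 only | 21% | 23% | 5% |
| r_w = 0.2 and δ = 0.5 | 57% | 63% | 19% |

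Sequence adjustment removes the period artefact but not the shared visit noise.

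**Both clauses of Hypothesis 3 together, inert drug.** A positive significant dSAT effect occurs in about 2.5% of trials. Under normality it is independent of the sample correlation, so the joint rate is roughly 0.025 × 0.41 = 1% at r_w = 0.3. Simulation gave 0.8–0.9% there and 2.0% at r_w = 0.5. It cannot exceed about 2.5%.

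**Both clauses, real mean effects but unlinked responses.** Give every patient a 0.4 SD gain on both outcomes, so individual responses do not vary and cannot be linked. At N=33 dSAT power is about 81%, and 0.81 × 0.41 = 33%; simulation gave 32–33%. At r_w = 0.2 it is 15–16%, at r_w = 0.1 about 6%, and at r_w = 0 about 2%. At N=38 and r_w = 0.3 it is 39%.

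**Off-drug reference.** Days 0 and 43 are both off drug if there is no carryover. Comparing the sequence-adjusted VCN-minus-placebo correlation with the day 0 to day 43 correlation by a Fisher z difference rejected in about 5% of inert-drug trials in every setting above. Its standard error at N=33 is √(1/29 + 1/30) = 0.260, so the 95% interval is about ±0.51 on the z scale. As a formal test it has about 6–9% power when true responses correlate at 0.61 and the response SD equals the mean effect (both assumed).

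**The case against.** Several objections have force.

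- **Hypothesis 3 is not the correlation alone.** A reader might infer that the whole hypothesis would be falsely confirmed in 9% to 41% of trials of an inert drug. The documents do not support that. The attention clause has its own mixed-model test, which holds joint false confirmation at or below about 2.5%.
- **No null is written down.** A reader might also infer that the plan prescribes an unadjusted Pearson test of zero. It does not. The protocol's Analysis Method bases analyses for all aims on mixed models, without saying how that would yield this correlation. The unadjusted test is the natural reading of an under-specified sentence, and nothing excludes it.
- **Status.** No confirmatory claim in the SAP rests on this analysis, and SAP 6.6 says secondary and exploratory p-values will be read cautiously. That lowers the stakes. The protocol nevertheless ties a mechanistic conclusion to the correlation.
- **The driving quantities are assumptions.** The Background statement concerns dual-task load, not off-drug co-fluctuation between visits, and the primary gait measure is taken without a dual task. The protocol says dSAT needs little training, and a baseline session precedes both treatment assessments, so large practice shifts may be unlikely. Splitting testing over two days, allowed for some patients, could weaken shared noise. With both quantities at zero the unadjusted test is valid.
- **Share of noise.** One might say that the plan's correlations show change scores to be mostly visit noise. They do not: a within-subject correlation does not by itself separate noise from individual response.
- **The comparison is weak.** With 6–9% power, making support for the clause depend on a significant difference would almost never succeed. This stands, and is why the comparison should be reported with its interval and not used as a pass/fail test.

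**Conclusion.** The concern holds for the correlation clause of Hypothesis 3. As described, the analysis cannot separate linked drug responses from shared visit fluctuation or period shifts. Its false-positive rate at N=33 with no drug effect is about 9% to 41% for assumed same-visit correlations of 0.1 to 0.3, and about 21% for a period shift of 0.5 SD of the paired difference on both outcomes. Smaller period shifts matter little.

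The practical exposure lies in the outcome that the trial hopes for. If varenicline improves both dSAT and gait on average, the attention test gives little protection: about 33% of trials would show both a dSAT effect and a correlation with no link between responses, given r_w = 0.3 and uniform 0.4 SD effects. These figures rest on normal outcomes, the plan's within-subject correlations and the stated assumptions. They show a plausible range, not an estimate for this trial. The tests of mean treatment effects are not affected.

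**What to change.** Add the analysis to the SAP with these elements:

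1. Define change as the VCN-minus-placebo difference (day 22 and day 64 visits) and name the attention measure, since Hypothesis 3 names SAT, the Procedures name dSAT, and the SAP ranks them differently.
2. Compute the correlation adjusted for treatment sequence, separately for gait speed and JERK, stating the expected sign for each.
3. Report beside it the same correlation for the off-drug change from day 0 to day 43, with a confidence interval for the difference.
4. Label the VCN correlation descriptive, and do not treat its own significance as evidence of an attentional mechanism.

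The cost is SAP wording and a few lines of code; all four visits already collect the data. There are two downsides. The interval for the difference will be wide at this sample size, so the result will often be inconclusive. The day 43 reference also depends on the plan's assumption of no carryover after the three-week washout.
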